For our needs assessment, we will obtain a list of caregivers involved with the specialized foster care program in DCFS as well as their contact information through the data sharing agreement in place between DCFS and Northwestern. We will attempt to recruit families through email first, then following up with a call, and then sending the survey and recruitment materials to the home. If we are not able to reach the caregivers, we will reach out to the youth's caseworker to facilitate our connection with the caregiver. For families we know do not easily engage with email, we will focus our recruitment efforts on calling and sending mail. Caregivers will be allowed to respond in any way that meets their needs.

For our pilot study, we will work with the Medical Director and the Psychology & Psychiatry Assistant Program Administrator at DCFS to identify caregivers who they believe could benefit from this program as well as organizations that serve foster parents who could connect us to interested families. Once these families have been identified and their contact information has been received by DCFS staff, we will reach out to the caregivers via phone, email, or text to see if they would be interested in participating in this pilot program. If they are interested, a member of the research team will meet with the family via phone or video-based conferencing to discuss the program and to obtain consent. This meeting will also be used to ensure that the family can participate in the intervention. If any of the initial families do not want to participate, or if they are found to be ineligible, we will work with DCFS staff to identify additional families who meet the criteria until we have achieved our desired sample size. Additionally, we will post recruitment information on social media online platforms (Facebook, Reddit, Craigslist, etc.). Potential subjects will be asked to complete a screening questionnaire via REDCap survey that goes over the eligibility criteria for our study. Potential subjects will also be asked to provide us with their contact information at the end of the screening questionnaire (name, email address/phone number).

5.0 Research Locations:

All study interventions will take place virtually. Study staff will meet with participants via Zoom, all data will be collected via REDCap, and data will be converted into reports to share with caregivers. All software used will be part of Northwestern's resources.

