Given that the pilot study will be working with caregivers of children with mental health issues and who are involved with the child welfare system, we will be monitoring the responses caregivers provide for potentially harmful situations during every interaction with research staff. Research staff will immediately make note of any potential issues during and after their interactions with participants, responding appropriately given the situation. Protocols have been developed for managing disclosures of child abuse or neglect as well as responding to indications of suicidality by the caregiver or youth. If research staff identify a need for more comprehensive mental health services, caregivers will be referred to the Service Provider IDentification & Exploration Resource (SPIDER) through DCFS to identify additional resources. In addition, the family's case worker will be notified of the increased need. If there is a direct risk to the child or caregiver's wellbeing, the proper authorities will be alerted. In addition, if the risk for or perpetration of abuse or neglect is suspected, research staff will immediately report relevant information to DCFS. If parents reveal any level of suicide risk, the youth's case worker

and, if necessary, emergency services will be immediately contacted. To promote full transparency, these potential breaches of confidentiality will be included in the consent form.

20.0 Long-term Data and Specimen Storage and Sharing:

All data collected from this study will be stored on FSM-approved drives. These include the REDCap server, as REDCap will be used to collect the data, and the FSM M-drive under the MHSPP folder. Because the participants are being hand-picked for this study and will be monitored over a period of time, data will have identifiers attached. However, only study staff will have access to identifiable data.

21.0 Qualifications of Research Team to Conduct the Research:

[name] is an Assistant Professor and Associate Director of the Mental Health Services and Policy Program at Northwestern University Feinberg School of Medicine. [name] research focuses on violence prevention, child welfare, parenting, and access to parenting and mental health promotion services for underserved children and families. [name] studies parenting interventions designed to promote positive parenting and prevent child physical abuse (CPA) through the use of innovative technologies.

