Cover Page

Study: PROACTIVE Parent: PROviding Access To InnoVative & Evidence-Based Intervention

Date: 6/16/21

Statistical Plan

We plan to enroll 14 foster parents with 7 foster parents per condition.

For the primary outcomes: acceptability, usefulness, and feasibility we will conduct descriptive analyses separately for the post-session items and the post-intervention Customer Satisfaction Survey. We will sum relevant items on the post-session questionnaires (administered after each of the 10 sessions) and provide mean ratings for program Acceptability, Usefulness, and Feasibility. We will provide mean ratings for Acceptability, Usefulness, and Feasibility from the Customer Satisfaction Survey. We will also provide descriptive statistics for other aspects of Feasibility as described below.

For the primary Treatment vs. Control group analyses we will examine 2 (Group) x 2 (Time) repeated measures ANOVA, with repeated measures on the second factor (Time). For measures that include subscales we will use K (number of subscales) x 2 repeated measures MANOVA to assess for treatment effect on subscale scores. For the child outcome measures we will use 2 x 2 repeated measures MANOVA with each of the child outcome measures and/or subscale scores in one model, as the child outcomes may share some variance.

For the delayed treatment analyses, we will combine the treatment and the delayed treatment participants to examine a one-way repeated measures ANOVA examining the pre-post scores of each of the groups – essentially using T1 and T2 data for the original treatment group and the T3 and T4 data for the delayed treatment groups. We will use a one-way repeated measures MANOVA for the child outcomes.

Primary Outcomes. Primary Outcomes will be assessed with three types of measures. Post-session measures that assess session content and delivery at the end of each of the 10 sessions, post-intervention in a Customer Satisfaction Survey, and pre- and post-intervention with standardized measures.

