Parent-Patient Activation Measure – Mental Health (P-PAM-MH). We will examine change in parent activation from baseline (T1) to post-treatment (T2, week 11) in the treatment condition relative to the control condition. Parent activation will be measured using the Parent-Patient Activation Measure- Mental Health. While the study is likely not powered to detect significant differences, our goal is to estimate effect sizes. We predict that parent scores in the treatment group, relative to the control group, will increase from baseline to Time 1 (T1) to post-intervention, while scores in the control condition will remain the same from baseline (T1) to T2, week 11. We predict that parents in the delayed treatment group will demonstrate consistent scores on T1, T2 and T3 (re-assessment, prior to delivery of delayed intervention) will remain the same, but that parents will demonstrate higher scores on T4 after receiving the delayed intervention.

Family Empowerment Scale (FES). We will examine change in parent empowerment from baseline (T1) to post-treatment (T2, week 11) in the treatment condition relative to the control condition. Parent empowerment will be measured using the FES. While the study is likely not powered to detect significant differences, our goal is to estimate effect sizes. We predict that parent scores in the treatment group, relative to the control group, will increase from baseline to Time 1 (T1) to post-intervention, while scores in the control condition will remain the same from baseline (T1) to T2, week 11. We predict that parents in the delayed treatment group will demonstrate consistent scores on T1, T2 and T3 (re-assessment, prior to delivery of delayed intervention) will remain the same, but that parents will demonstrate higher scores on T4 after receiving the delayed intervention.

Secondary Outcomes.

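### The SAP compares treatment with control, but neither document says how parents are assigned to a condition, and the protocol describes no control arm

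*SAP*

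**What the plan says.** The SAP (Statistical Plan, dated 6/16/21) sets the size and split: "We plan to enroll 14 foster parents with 7 foster parents per condition". Its between-group analysis is "For the primary Treatment vs. Control group analyses we will examine 2 (Group) x 2 (Time) repeated measures ANOVA". Each standardized measure is then described as change "from baseline (T1) to post-treatment (T2, week 11) in the treatment condition relative to the control condition". Two of these measures, the P-PAM-MH and the FES, stand under Primary Outcomes. The stated purpose is estimation: "While the study is likely not powered to detect significant differences, our goal is to estimate effect sizes". For the delayed-treatment phase, "we will combine the treatment and the delayed treatment participants to examine a one-way repeated measures ANOVA examining the pre-post scores", taking T1 and T2 from the first group and T3 and T4 from the delayed group.

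The protocol (version 12/08/2021) describes a different study. Section 3.0 has 50 caregivers, all receiving the intervention. Section 8.0 has one assessment before the sessions and one after the last. Sections 2.0, 4.0, 8.0 and 11.0 cover eligibility, recruitment, procedures and consent without mentioning a control group, a waiting period or an assignment step.

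On entry to the study, section 4.0 has agency staff identify caregivers they think could benefit. If some decline or are ineligible, "we will work with DCFS staff to identify additional families who meet the criteria until we have achieved our desired sample size". The same section adds recruitment through social media. Section 20.0, on data storage, says "Because the participants are being hand-picked for this study and will be monitored over a period of time, data will have identifiers attached".

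**The concern.** A Group x Time contrast can be read as a program effect only if the groups would have changed alike without the program. Random assignment secures that in expectation. Here no rule is given, so nothing in the plan prevents urgency, availability or recruitment route from deciding who starts and who waits. If families whose T1 scores are temporarily poor tend to start first, those scores will drift back toward their usual level, and the contrast will credit the drift to the program.

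This matters even though the SAP disclaims power. Its product is an effect size, and the protocol's two aims ask whether the program improves parent capacity and youth symptoms. A confidence interval shows imprecision but not bias.

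**Working it through.** **1. The plan's own figure.** 7 + 7 = 14 agrees within the SAP. It does not agree with the protocol's 50. The SAP gives no alpha, SD, effect size, power or dropout rate, so there is no sample-size calculation to reproduce.

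**2. Search for an assignment rule.** No form of the word random appears in the available text of either document, and no other rule is given. The SAP names no baseline adjustment. The consent forms were not available.

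**3. Size of a false contrast.** Let g be the T1 gap between groups in baseline SDs, arising from selection on the T1 score, and r the T1–T2 correlation. With equal SDs and no true effect:

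- false difference in change = (1 − r) × g baseline SD
- SD of change = √(2(1 − r)) baseline SD
- 95% half-width with 7 per group = t(0.975; 12 df) × √(2/7) = 2.1788 × 0.5345 = 1.165 SD of change

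The documents give neither g nor r. Assuming g = 0.5 and r from 0.5 to 0.8:

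| r | SD of change (baseline SD) | False contrast (baseline SD) | False contrast (SD of change) | 95% half-width (baseline SD) |
|---|---|---|---|---|
| 0.5 | 1.00 | 0.5 × 0.5 = 0.25 | 0.25 | 1.165 |
| 0.6 | 0.89 | 0.4 × 0.5 = 0.20 | 0.22 | 1.042 |
| 0.7 | 0.77 | 0.3 × 0.5 = 0.15 | 0.19 | 0.902 |
| 0.8 | 0.63 | 0.2 × 0.5 = 0.10 | 0.16 | 0.737 |

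Doubling g to 1.0 doubles the false contrast, to 0.20–0.50 baseline SD.

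**4. Simulation with no true effect.** There were 10,000 replicates per scenario, with r = 0.5, 0.7 and 0.8. The 14 parents were drawn from the worse half of a normal symptom distribution; units are SDs of that full distribution.

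| How the 7 early starters are chosen | False Group x Time difference | Rejections at 5% |
|---|---|---|
| At random | about 0.00 | 5% |
| Higher need tends to start first | 0.13–0.33 | 6–9% |
| The 7 highest-need start first | 0.18–0.44 | 8–14% |

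**5. The pooled pre-post analysis.** In the same simulation it showed a false improvement of 0.16–0.40 SD (14–33% rejections), however the groups were formed. That treats every parent's pre score as the one selected on. Delayed parents contribute T3, by which time the drift may be over. If they contributed none, the figure would halve to 0.08–0.20 SD.

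**6. Randomisation alone does not balance 14 parents.** The chance T1 gap has SD √(2/7) = 0.53, so a gap of at least 0.5 SD in either direction has probability 2 × [1 − Φ(0.5/0.5345)] = about 0.35. Adjustment for T1 is therefore useful even with random allocation.

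**The case against.** **Silence is not non-random assignment.** A reader might infer from "Because the participants are being hand-picked for this study" that the groups were formed by choice. The documents do not support that. The phrase explains why identifiers are kept, and it concerns entry to the study, as does the text on replacing families. Selection at entry acts on both groups and largely cancels in the Group x Time contrast. Nor is everyone chosen by staff, since caregivers may come forward through social media. This objection stands in full: the supportable finding is that no assignment method is stated.

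**The bias may be near zero.** The formula needs the gap to come from selection on the T1 score. If early starters differ stably in need, no regression to the mean is expected in the change contrast. This also stands, so the range above is conditional.

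**Analysts could adjust later.** In part. If selection is on the observed T1 score, a T1 covariate removes the bias. If the groups differ stably, the change score is unbiased and the covariate itself introduces an error of g − r × g = (1 − r) × g, in the opposite direction. Which analysis is right depends on how the groups were formed, which is the missing fact. Neither removes unmeasured confounding.

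**Imprecision is larger than the bias.** True, but the bias shifts the estimate without widening the interval.

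**The SAP may simply be out of date.** It predates the protocol version by about six months, and the design may have changed. In that case its contrast has no design behind it; otherwise the assignment rule is undocumented. Either way a correction is needed.

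**The reach is limited.** Acceptability, usefulness and feasibility are summarised descriptively and are not a group contrast. The protocol says its pilot data will inform a larger study, but the SAP does not say that this particular estimate will plan it.

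**Conclusion.** The concern holds as a gap with consequences: the SAP's treatment-versus-control comparison rests on two groups for which neither document gives an assignment rule, and the protocol describes only one treated group. Under an assumed 0.5 SD gap from selection on T1 and r of 0.5–0.8, the false contrast is 0.10–0.25 baseline SD, or 0.16–0.25 SD of change against a half-width of 1.165. It is near zero if the groups differ stably in need. The direction assumes that worse-scoring families start first, which no document states.

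The stronger conclusion that assignment is non-random, or that selecting participants for the study biases the group contrast, does not follow. Selection at entry bears most directly on the pooled pre-post analysis and on the protocol's single-group comparison, which have no concurrent control. Random assignment would not cure either.

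**What to change.** Decide first which design is being run, then make both documents describe it.

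- **If there are two conditions:** state that, after consent and completion of T1, parents are allocated 1:1 to immediate or delayed treatment by a computer-generated sequence concealed from recruiters and coaches (REDCap could hold it). Analyse parents as allocated, with T1 as a covariate. Reconcile the protocol with the SAP on arms, sample size (14 or 50), the T1–T4 assessments and consent wording.
- **If allocation will not be random, or there is no control arm:** name the actual rule and label the comparison non-randomised, or remove it. Drop the causal wording.
- **In either case:** label the pooled pre-post analysis as uncontrolled.

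The cost is amended wording and allocation set-up, with no parents beyond the SAP's 14. The protocol must also add the delayed-arm assessments that the SAP already assumes, which is more than a wording change. Some families whom staff would like to start at once will wait. The rule must be settled before any parent is assigned, because later adjustment cannot be relied on to repair it.

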In addition to creating the infrastructure and content necessary to support PROACTIVE Parent, this study ultimately has two aims:

1. Does the PROACTIVE Parent Program improve foster parents' capacity for supporting their youth in care's mental wellbeing?
2. Does the PROACTIVE Parent Program improve youth in cares' mental health symptoms, as reported by the foster parents?

2.0 Enrollment Criteria (who can be in your study and who would not be eligible to participate in your study):

For the needs assessment, eligible participants are foster parents of youth with a special health care need (including disabilities, mental health needs, and/or complex medical needs). Participants must be over the age of 18 and be actively fostering a child through the Illinois Department of Children and Family Services.

For the pilot study, eligible participants are foster parents of youth with identified mental health needs. Foster parents must be over the age of 18 and be actively fostering a child ages 5-13 through a child welfare agency in the United States. All participants will also need to speak English, be a resident of Illinois, and be able to navigate virtual meeting technologies (e.g. Zoom).

3.0 Sample Size:

For our needs assessment, we anticipate that 1000 caregivers involved in the specialized foster care program will complete our survey. Given that over 3000 caregivers foster youth in care with special health care needs, we believe that this is a feasible number with recruitment support from DCFS.

For our initial pilot study, we will be recruiting 50 caregivers who will receive the pilot intervention. This pilot data will be used to inform a larger iteration of the study, but we believe that 50 caregivers is sufficient for our initial pilot.

4.0 Recruitment and Screening Methods:

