At the same time, the research team will pilot the initial iteration of the PROACTIVE parent model with foster parents of youth in the foster care programs. After foster parents complete an initial screening via REDCap survey, a member of the research team will contact the foster parent to confirm eligibility. The research team member will then obtain informed consent. After consent has been given, the foster parents will be asked to complete an initial and final assessment. Initial assessment is completed prior to attendance of parent coach sessions and the final assessment is completed after the last session.

The subjects will complete a demographics questionnaire (i.e. name, age, sex, gender, race, ethnicity, education, employment, socioeconomic status, address (for mailing payment, confirmation of state residency, and mailing consent form if requested), caseworker contact information) as part of their initial assessment. We will also ask subjects questions regarding their own parenting needs, their youth's mental health needs, and the parents' ability for engaging with mental health services.

During this initial and final assessment, the parent will complete the following measures:

- Parent-Patient Activation Measure – Mental Health
- PROMIS Parent Proxy Measure – Anxiety
- PROMIS Parent Proxy Measure – Depression
- Pediatric Symptom Checklist-17 (Parent Proxy)
- Barriers to Treatment Participation Scale
- Client Satisfaction Questionnaire (final assessment only)

Data will be collected through a REDCap survey.

Parent involvement in the intervention is anticipated to be 30-60 minutes each session (up to 10 sessions) which may occur over the course of up to 12 weeks.

Foster parents will be compensated \$20 after completing the initial assessment *and* attending the initial session. Foster parents will also be compensated \$20 after completing the final assessment. In addition, foster parents will have the ability to earn

continuing education credits necessary for foster parent licensure for completing this program.

Following the initial assessment, the caregiver will meet with a parent coach, who is an internal member of the NU research team, for 30-60 minutes each session. The content of the sessions will consist of one or more of the following:

- 1) introducing the program
- 2) identifying and setting goals
- 3) discussing results of the assessment
- 4) helping parents develop literacy regarding their child(ren)'s mental health needs

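### The 2 x 2 repeated measures ANOVA fixes the T1 slope at 1; under random allocation, adjusting T2 for T1 gives tighter effect sizes when the T1-T2 correlation is below about 0.8

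*SAP*

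**What the plan says.** The SAP's Statistical Plan sets the size and the between-group method. The size is given as "We plan to enroll 14 foster parents with 7 foster parents per condition". The method is a "2 (Group) x 2 (Time) repeated measures ANOVA, with repeated measures on the second factor (Time". Measures with subscales get a repeated measures MANOVA. For the child measures the text reads "For the child outcome measures we will use 2 x 2 repeated measures MANOVA", on the ground that those outcomes may overlap in variance.

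Each standardised measure then has its own paragraph defining the effect as T1-to-T2 change relative to control. For parent activation the wording is "We will examine change in parent activation from baseline (T1) to post-treatment (T2, week 11) in the treatment condition relative to the control condition". Each of these paragraphs also states the aim: "While the study is likely not powered to detect significant differences, our goal is to estimate effect sizes".

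Neither document uses T1 as a covariate. Neither gives a T1-T2 correlation, an outcome SD, an alpha, a target effect or a power figure. The supplied text does not say how parents are assigned to conditions.

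Protocol section 8.0 confirms that the baseline precedes treatment: "Initial assessment is completed prior to attendance of parent coach sessions and the final assessment is completed after the last session".

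**The concern.** When estimation is the goal, the width of the interval is what counts. A two-occasion repeated measures ANOVA subtracts the whole T1 score from T2. Unless the true slope of T2 on T1 is 1, that subtracts too much, adds noise, and leaves the estimate sensitive to whatever T1 gap the allocation produced. With 7 parents per arm, such gaps can be large.

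The SAP already plans a T1 score for every standardised measure, including P-PAM-MH and FES, which it lists among the primary outcomes. A model that estimates the slope therefore needs no new data. At stake are the precision of the reported effect sizes and how far a single trial's estimate depends on its own baseline imbalance.

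**Working it through.** **Inputs from the SAP.** 7 per condition, N = 14; two occasions, T1 and T2 (week 11); no baseline covariate.

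**Assumptions, because the documents give no values.** Random allocation; equal SDs at T1 and T2 (set to 1, so results are in SD units); no dropout; T1-T2 correlation rho from 0.3 to 0.9. There is no stated power or precision figure to reproduce.

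**Step 1: what the ANOVA tests.** On simulated data with 7 per arm, the Group x Time F was 1.314 and the squared t on change scores was 1.314. They are the same test, with 12 error df.

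**Step 2: variance of the group effect.**
- Change score: (2/n) x 2(1 - rho), with 12 df.
- T1-adjusted: (2/n) x (1 - rho²) x [1 + 1/(N - 4)], with 11 df. At N = 14 the bracket is 1 + 1/10 = 1.1, the small-sample cost of estimating the slope.
- Ratio, adjusted to change: 1.1 x (1 + rho)/2.

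At rho = 0.5 the change-score SE is sqrt(0.2857 x 1.00) = 0.535. The adjusted SE is sqrt(0.2857 x 0.75 x 1.1) = 0.486. The ratio is 1.1 x 0.75 = 0.825.

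| rho | SE, change | SE, adjusted | Variance ratio | 95% CI half-width, change | 95% CI half-width, adjusted | Parents per arm the change score would need to match |
|---|---|---|---|---|---|---|
| 0.3 | 0.632 | 0.535 | 0.715 | 1.38 | 1.18 | 9.8 |
| 0.5 | 0.535 | 0.486 | 0.825 | 1.17 | 1.07 | 8.5 |
| 0.7 | 0.414 | 0.400 | 0.935 | 0.90 | 0.88 | 7.5 |
| 0.8 | 0.338 | 0.336 | 0.990 | 0.74 | 0.74 | 7.1 |
| 0.9 | 0.239 | 0.244 | 1.045 | 0.52 | 0.54 | 6.7 |

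The last column is 7 divided by the variance ratio. A simulation of 60,000 trials per correlation gave SDs of the estimates within 0.003 of these SEs.

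**Step 3: where the gain ends.** Setting 1.1 x (1 + rho)/2 = 1 gives rho = 2/1.1 - 1 = 0.82. For interval width, where the lost df also counts, the break-even is about 0.78.

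**Step 4: chance baseline gaps.** Under random allocation the T1 mean difference has SD sqrt(2/7) = 0.53. Since 0.5/0.53 is about 0.94, roughly 35% of allocations give a gap above 0.5 SD in one direction or the other. Given a gap (treatment minus control), the change-score estimate is off by -(1 - rho) x gap. For a gap of 0.53 SD the size of the shift is 0.37, 0.27 and 0.16 SD at rho 0.3, 0.5 and 0.7.

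In simulation with a true effect of 0.50, rho 0.5 and a gap near +0.53, the change score averaged 0.24 and the adjusted estimate 0.50. A gap of the opposite sign inflates the estimate by as much. Over all allocations, both methods averaged 0.50.

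**Step 5: power, for scale only.** For a 0.8 SD effect at rho 0.5 (two-sided 5%, noncentral t), power is 28% for the change score and 33% adjusted.

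**The case against.** The strongest reply is that the planned analysis is standard and valid, and that it answers the stated question, change relative to control. This stands: preferring the adjusted model is a matter of efficiency. The question does not change, however. Regressing T2 or T2 - T1 on group and T1 gives the same group coefficient.

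A second reply is that everything above presupposes random allocation, which the supplied text does not state. This also stands. Without randomisation the two analyses target different quantities, and the adjusted one may be the biased one. A reader might infer non-random assignment from Protocol section 20.0, which describes participants as individually chosen, but that remark concerns entry to the study and not assignment to condition. The Protocol adds doubt of another kind: section 3.0 says "we will be recruiting 50 caregivers who will receive the pilot intervention" and describes no control group. That must be reconciled with the SAP's 7 versus 7.

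Third, the size rests on an undocumented correlation and on equal SDs. At 0.7 the interval narrows by only about 2%, and at 0.9 the change score is slightly better. If T2 varies more than T1, the true slope rises and the gain shrinks. So the planned analysis cannot be called less precise without qualification.

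Fourth, replacing the MANOVAs outright would ignore the SAP's shared-variance reason for them. This is accepted, and the fix keeps them. It is also true that the Protocol's assessment list in section 8.0 omits FES and DERS, so for those two the T1 score rests on the SAP alone.

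**Conclusion.** The point holds as a conditional, modest gain in precision. Given random allocation, similar SDs and a correlation below about 0.8, adjusting T2 for T1 estimates the same effect with 28.5%, 17.5% or 6.5% less variance at correlations of 0.3, 0.5 or 0.7. It also removes the conditional error caused by a chance T1 gap. Near 0.8 there is nothing to gain, and at 0.9 there is a small loss.

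Three stronger readings are tempting and unsupported:
- That the ANOVA is biased. Averaged over random allocations it is not; the error is conditional on the gap and can hide an effect as easily as inflate one.
- That a larger trial would be sized on this estimate. Protocol section 3.0 says only that the pilot data will inform a larger iteration, and no sample size or go/no-go rule is tied to it.
- That adjustment rescues the sample size. At correlation 0.5 the half-width goes from 1.17 to 1.07 SD, still about 1 SD.

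This is a cheap improvement to a plan that says "our goal is to estimate effect sizes".

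**What to change.** First state in the SAP how parents are allocated. If allocation is random:
- For the P-PAM-MH, FES, BTPS and DERS totals, and for each child score, make the main effect-size estimate the group coefficient from a linear model of T2 on group and T1. Report it with its 95% CI and as a standardised value.
- Keep the planned 2 x 2 ANOVA as a sensitivity analysis.
- Keep the planned MANOVAs for the joint child-outcome and subscale tests. The separate child-score models then supply estimates and intervals and do not replace the joint tests.

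If allocation is not random, do not make this change on the present argument.

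The cost is SAP wording, one error degree of freedom (12 to 11, already counted in the figures above), and a trivial loss of precision if the correlation exceeds about 0.8. No data are needed beyond the T1 and T2 scores the SAP already plans.
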